## 10.2 Adverse events

Adverse events are recorded on the AE CRF as they occur, from the time informed consent is granted until study completion or study termination (end of the SFU period 30 days after the last IMP intake). All AEs will be coded using the latest available version of MedDRA.

A treatment-emergent adverse event (TEAE) is defined as any event not present prior to the initiation of the first dose of study treatment or any unresolved event already present before initiation of the first dose that worsens in intensity following exposure to the treatment. The number and percentage of subjects who experience TEAEs at any time during the study will be summarized by SOC and PT. The following tabular summaries will be presented for the SS:

- Incidence of pre-treatment AEs. Pre-treatment AEs are AEs with start dates prior to the date of first dose of IMP.
- Incidence of TEAEs during the Treatment Period – Overview. Of note, the corresponding table is required for data transparency reporting.
- Incidence of TEAEs by period (Treatment Period, Titration and Stabilization Period, Maintenance Period, Conversion Period, and Taper and SFU Period)
- Incidence of Serious TEAEs by period (Treatment Period, Titration and Stabilization Period, and Maintenance Period)
- Incidence of TEAEs leading to discontinuation by period (Treatment Period, Titration and Stabilization Period, and Maintenance Period)
- Incidence of TEAEs leading to dose reduction during the Stabilization Period

The following will be presented for TEAEs during the overall Treatment Period:

- Subject numbers for TEAEs
- Incidence of TEAEs occurring in at least 5% of subjects in any treatment group

- Incidence of TEAEs occurring in at least 2% of subjects in any PSL group and greater than placebo group
- Incidence of TEAEs by Relationship
- Incidence of TEAEs by Maximum Intensity
- Incidence of TEAEs of special interest
- Incidence of SAEs by Relationship. Of note, the corresponding table is required for data transparency reporting.
- Incidence of Fatal TEAEs by Relationship. Of note, the corresponding table is required for data transparency reporting.
- Incidence of Non-Serious TEAEs above the threshold of 5% of subjects in any treatment group. Of note, the corresponding table is required for data transparency reporting.
- Summary of the duration in days per event for the following TEAEs: somnolence, dizziness, fatigue, irritability and headache. In this analysis, if an AE is ongoing, the duration will be calculated till the date of final contact.

Summaries will be presented based on standard Sponsor AE table formats and considering formats used for the PSL program.

Where dates are missing or partially missing, AEs will be assumed to be treatment-emergent, unless there is unmistakable evidence (through comparison of partial dates, see Section 4.2) to suggest that the AE started prior to the first dose of study treatment. Summary tables will contain counts of subjects, percentages of subjects in parentheses and the number of events where applicable. A subject who has multiple events in the same MedDRA category (SOC or PT) will be counted only once in the subject count for that category, however all events will be included in the event count for the category. In summaries including relationship to study treatment, the following relationships will be summarized: 'Not related', 'Related'. A subject may be counted more than once according to the relationship to study treatment. Events with missing relationship will be considered as 'Related' to the last given study product for summary purposes but recorded as missing in the listings. In summaries of the maximum intensity, the following intensity categories will be summarized: 'Mild', 'Moderate', 'Severe'. Subjects who experience the same event multiple times, with differing severities, will be included in the most severe category. Events with missing intensity will be considered as 'Severe' events for summary purposes but recorded as missing in the listings. The main reasons for treatment discontinuation will be listed by subject. The daily dose of study medication corresponding to the AE onset date will be included in the listing. Daily dose will be derived from 'Study Medication Administration' CRF.

Adverse event summaries will be ordered in terms of decreasing frequency for SOC, and PT within SOC, within the PSL total group column.

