7.2.3 Conversion Period

In case the subjects wish to proceed to the OLE study, the treatments and doses will be adjusted gradually in a blinded way to reach the single-entry dose into the OLE study (PSL 400mg/day) as presented in Table 7-4. During the Conversion Period, the dose of IMP must always be administered as bid morning and evening doses, approximately 12 hours apart.

Subjects taking placebo will be converted to active PSL.

Table 7-4: Conversion Period dosing

Dose Arm	Dose per day (morning-evening) during conversion		
	Week:	Week 16	Week 17
PSL 800mg/day	300-300	200-200	200-200
PSL 600mg/day			
PSL 400mg/day	200-200		
PSL 300mg/day			
PSL 200mg/day	100-100	150-150	200-200
PSL 150mg/day			
PSL 100mg/day	50-50	100-100	150-150
PSL 50mg/day			
Placebo			

OLE=open-label extension; PSL=padsevonil

After completion of Week 18, the dose will be 200-200, the entry dose in the OLE study, EP0093.

Note: Dose adjustments steps may vary in length by ± 3 days per week while overall Conversion Period length should not change by more than 1 week.

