## **2.4 Safety variables**

### **2.4.1 Primary safety variables**

The safety variables are as follows:

- Incidence of TEAEs reported by the subject and/or caregiver or observed by the Investigator during the entire study
- Incidence of TEAEs leading to study withdrawal
- Incidence of treatment-emergent serious adverse events (SAEs) during the entire study

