#### Conversion Period (3 weeks)

The 3-week Conversion Period will be required for subjects who choose to enroll in the OLE study at the end of the Maintenance Period. Doses for subjects participating in the 3-week Conversion Period will be gradually adapted (increased or decreased) in a blinded way to reach the entry dose for the OLE. Subjects who took placebo during the maintenance phase will progressively receive PSL.

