### **2.6.2 Study duration per subject**

The total duration of study per subject will be up to 27 weeks with a maximum of 19 weeks exposure to PSL. An additional follow-up echocardiogram will be performed at 6 months ( $\pm 1$  month) after the last IMP intake only for subjects exposed to IMP for more than 3 weeks and either discontinuing the study or not entering the OLE.

The end of the study is defined as the date of the last SFU Visit (30-days after the last IMP intake) of the last subject in the study. Additionally, the reporting of SAEs will continue until the 6-month follow-up echocardiogram.

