## 3 DATA ANALYSIS CONSIDERATIONS

### 3.1 General presentation of summaries and analyses

Statistical analysis and generation of tables, figures, subject data listings, and statistical output will be performed using SAS Version 9.3 or higher. All tables and listings will use Courier New font size 9.

Descriptive statistics will be displayed to provide an overview of the study results. For categorical variables, the number and percentage of subjects in each category will be presented. Unless otherwise noted, all percentages will be displayed to 1 decimal place. No percentage will be displayed for zero counts, and no decimal will be presented when the percentage is 100%. For continuous variables, descriptive statistics will include number of subjects with available measurements (n), mean, SD, median, minimum, and maximum.

Decimal places for descriptive statistics will always apply the following rules:

- “n” will be an integer
- Mean, SD, and median will use one additional decimal place compared to the original data
- Minimum and maximum will have the same number of decimal places as the original value.

Unless otherwise specified, statistical tests of efficacy variables will be presented as two-sided p values rounded to three decimal places. P-values less than 0.001 will be presented as “<0.001” and p-values greater than 0.999 will be presented as “>0.999.” Statistical comparisons will be two-sided and will be performed at the 0.05 level of significance.

A complete set of data listings containing all documented data as well as calculated data (e.g., change from Baseline), as applicable, will be generated.

Treatment groups will be displayed as: Placebo, PSL 50 mg bid, PSL 100mg bid, PSL 200mg bid, and PSL 400mg bid.

Log-transformation is based on natural logarithm. For analyses on log-transformed values, model estimates will be back-transformed to anti-log space for table presentation. See Section 8.1.1 for details.

Data collected at scheduled visits will be included the by-visit summary. Data collected at unscheduled visits will not be included in the by-visit summary, but will be considered when determining the Last Visit, minimum, and maximum post-Baseline values during the Treatment Period. Data collected on Visit 8 will be summarized separately for subjects in the Conversion Period versus the Taper and Safety FU Period.

In general, all CRF data will be presented in the subject listings.

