**Table 3–1: Start and end of EP0091 analysis periods**

Analysis Period			Details
Description	Start	End	
Baseline (Week -4)	Date of informed consent at Visit 1	Date of the day before the date of Visit 2.	This is an approximate 28-day period for calculation of Baseline seizure frequencies. Study drug is dispensed, and first dose is generally taken the day of the Baseline Visit (Visit 2, Day 1). Note the pre-dose assessments will also be included in the Baseline Period.
Titration and Stabilization*	The date of the Baseline Visit, (Visit 2, Day 1).	The date of the day before Visit 4 or the end of the treatment period if the subject has discontinued prior to Visit 4.	For evaluation purposes, if results are presented by analysis period, the Titration and the Stabilization interval will be considered together (approximately 4 weeks in total). Titration is a period of dose increases to reach the protocol specified dose. Stabilization is an approximate week-long interval to stabilize at the target dose level. During stabilization the dose may be adjusted once (i.e. to a fallback dose).
Maintenance*	The date of Visit 4.	The date of Visit 7 or the end of the treatment period if the subject has discontinued prior to Visit 7.	This is a 12-week period where the subject remains on the randomized target dose (or fallback dose, if applicable).
16-week Treatment Period*	The date of the Baseline visit (Visit 2)	The date of Visit 7 or the end of the treatment period if the subject has discontinued prior to Visit 7.	Titration and Stabilization Period and Maintenance Period combined.
Conversion	The date of the day after Visit 7	The date of Visit 8.	This is a 3-week period of dose conversion to enable the subjects to enroll into the OLE study EP0093.
Taper and Safety Follow-up	The date of the day after Visit 7/EDV or the date of day after Visit 8 if the subject tapered after conversion	The date of final contact.	Subjects who withdraw from the study or decide not to participate in the OLE study will be tapered off the IMP during a 3-week period followed by a 1-week drug-free period. A SFU visit will be performed 30 days after the last IMP intake.

OLE=open-label extension; SFU=Safety Follow Up

\* Only seizure data prior to and on the date of last dose of study medication will be included in the analysis.

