## 10 SAFETY ANALYSES

The SS will be used to summarize and analyze all safety variables. In case of dosing administration error, summaries and analyses using the SS will be conducted according to actual treatment administered according to the rule described in Section 3.6. Safety data will be summarized for each treatment group and the PSL total group.

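### Adverse events that placebo subjects have on padsevonil during Conversion would be reported under Placebo, because the SAP has no attribution rule for them and its entire-study window does not match its tables

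*SAP*

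**What the plan says.** **Drug taken.** Subjects who choose the extension first pass through Conversion, of which SAP Table 3-1 says: "This is a 3-week period of dose conversion to enable the subjects to enroll into the OLE study EP0093." Protocol 7.2.3 is explicit: "Subjects taking placebo will be converted to active PSL." SAP 2.6.1 agrees: "Subjects who took placebo during the maintenance phase will progressively receive PSL."

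**Variable.** The first primary safety variable in SAP 2.4.1 is "Incidence of TEAEs reported by the subject and/or caregiver or observed by the Investigator during the entire study." Serious TEAEs carry the same window.

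**Analysis.** SAP 10.2 opens its tabulations with "The number and percentage of subjects who experience TEAEs at any time during the study will be summarized by SOC and PT" and then lists the tables. TEAEs are tabulated by period, and both Conversion and Taper/Safety Follow-up have their own entries. Serious TEAEs and TEAEs leading to discontinuation are tabulated only for Treatment, Titration/Stabilization and Maintenance. The overview and the common-event, relationship, intensity, special-interest and fatal-event tables cover the Treatment Period.

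**Columns.** SAP 3.1: "Treatment groups will be displayed as: Placebo, PSL 50 mg bid, PSL 100mg bid, PSL 200mg bid, and PSL 400mg bid." SAP 10: "Safety data will be summarized for each treatment group and the PSL total group." Under SAP 3.6 safety subjects are analysed as assigned, and only dosing errors receive special consideration. SAP 3.1 splits Visit 8 data into conversion and taper, but not by drug taken. Dose at onset of an adverse event goes into a listing only. SAP 10.1 summarises exposure for the 16-week Treatment Period only.

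**The concern.** The secondary objective is safety and tolerability relative to placebo, so the placebo column has to mean subjects on placebo. From the day after Visit 7 it does not. A placebo subject who enters Conversion is being brought onto padsevonil for the first time, by design and not through a dosing error, so nothing in SAP 3.6 moves that subject's events.

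Three things are at stake:

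- The Conversion table would present up-titration onto padsevonil as placebo experience, and PSL total would omit it.
- The primary safety variable is defined over a window in which the control arm is partly on active drug, and no listed table matches that window. A programmer working from the definition rather than the list would produce a contaminated comparison.
- No listed table covers a serious event in a newly exposed former-placebo subject during Conversion, and no exposure summary supplies its denominator.

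**Working it through.** **1. Is there padsevonil exposure in the placebo arm within this study?** The SAP states: "The total duration of study per subject will be up to 27 weeks with a maximum of 19 weeks exposure to PSL." 16 weeks of treatment + 3 weeks = 19 weeks, which reproduces the figure. The sum alone does not prove conversion exposure, because 16 weeks plus a 3-week taper also gives 19. The explicit statements in Protocol 7.2.3 and SAP 2.6.1 do. A placebo subject who converts therefore has about 3 weeks on padsevonil inside the entire-study window.

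**2. How many subjects?** The documents do not say. The nearest figure is in Protocol 2.3.1: 42 of 55 subjects in the proof-of-concept study entered its extension, and 42/55 = 76%. If that held here (an assumption), 0.76 × 80 ≈ 61 of the 80 planned placebo subjects would take padsevonil in Conversion.

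**3. Which planned outputs are affected?** By SAP Table 3-1 the Treatment Period ends at Visit 7 and Conversion starts the next day. Taper/Safety Follow-up can start after Visit 8 for subjects who taper after converting.

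| Output | Placebo column includes on-padsevonil data? |
|---|---|
| TEAE overview; common-event, relationship, intensity, special-interest and fatal tables | No, these stop at Visit 7 |
| TEAEs by period: Treatment, Titration/Stabilization, Maintenance | No |
| Serious TEAEs; TEAEs leading to discontinuation | No, but Conversion is not tabulated at all |
| TEAEs by period: Conversion | Yes, the whole column |
| TEAEs by period: Taper/Safety Follow-up | Yes, for subjects who taper after converting |
| Visit 8 conversion summaries (laboratory, vital signs, ECG) | Yes |
| Any table over the entire study | Yes |

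**4. What would an entire-study table show?** Let p be the 16-week incidence, f the share converting, and h the risk of a first event in Conversion among subjects still event-free. Then

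incidence over the entire study = p + (1 − p) × f × h.

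Placebo incidence can only rise. The padsevonil arms also add events, and Protocol Table 7-4 changes dose in several of them. With the same f in all arms, the difference shrinks only if

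h(PSL) / h(placebo) < (1 − p(placebo)) / (1 − p(PSL)).

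None of p, f or h is given in the documents. The assumed values are f = 50–90%, with (h placebo, h PSL) = (10%, 5%), (20%, 5%), (30%, 10%), (10%, 10%) or (10%, 15%).

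- *Any TEAE, 60% against 80% (20.0 points).* At f = 0.7, h = 20% and 5%: placebo 0.60 + 0.40 × 0.7 × 0.20 = 0.656; padsevonil 0.80 + 0.20 × 0.7 × 0.05 = 0.807; difference 15.1 points. The full range is 11.0 to 19.5 points, with about 2 to 9 extra placebo subjects out of 80. The break-even risk ratio is 0.40/0.20 = 2.0.
- *One preferred term, 8% against 25% (17.0 points).* At the same f and h: placebo 0.08 + 0.92 × 0.7 × 0.20 = 0.209; padsevonil 0.25 + 0.75 × 0.7 × 0.05 = 0.276; difference 6.7 points. The full range is −1.1 to 18.8 points, with about 4 to 20 extra placebo subjects out of 80. The break-even ratio is 0.92/0.75 = 1.23. At h = 10% and 15% the ratio is 1.5, so the difference widens: 0.329 − 0.144 = 18.4 points at f = 0.7.

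**The case against.** A reader might infer that the main drug–placebo TEAE comparison is biased towards no difference. The documents do not support that. The list in SAP 10.2 contains no entire-study table, and every table that would carry the comparison with placebo stops at or before Visit 7. The SAP's amendment history points the same way: Amendment 1 replaced a list specified over the entire study with by-period and Treatment Period tables, so the sentence quoted from 10.2 may simply have been left behind. Nor is a smaller difference certain even in a table over the entire study, as step 4 shows.

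It would also be too strong to say that the Conversion data are hidden. Conversion TEAEs have a table of their own, dose at onset is listed, and both documents state that placebo subjects receive padsevonil then.

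All of this stands, and it limits the point. It does not remove it. The Conversion table is planned, its columns are fixed by SAP 3.1 and 10, and followed literally they put the wrong treatment name over the data. The variable in SAP 2.4.1 still says entire study, so the definition and the outputs disagree. The sponsor's own description of the proof-of-concept study in Protocol 2.3 and 2.3.1, which had a similar placebo-to-drug switch, uses a placebo/PSL group and an on-PSL period. This SAP has neither.

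**Conclusion.** The point holds as a problem of attribution and of window definition, not as a demonstrated bias in the planned placebo comparison.

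What is established without any assumed rate: the Placebo column of the Conversion TEAE table consists of subjects being moved onto padsevonil; their events are left out of PSL total; the Visit 8 conversion summaries and any taper-after-conversion data share the wrong label; and the entire-study window of the primary safety variable includes this exposure. The listed Treatment Period tables are sound.

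The size and direction of the effect on an entire-study difference cannot be derived from the documents. The ranges in step 4 rest wholly on assumed incidences, an assumed share converting that is equal across arms, and assumed risks during Conversion. They show only that the effect could be material for a single preferred term and could go either way.

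**What to change.** - **SAP 2.4.1 and 10.2:** define the between-arm comparison for the primary safety variables over the 16-week Treatment Period for all subjects, and align the opening sentence in 10.2 with it. Because Protocol 4.2.1 uses the entire study, record this in SAP 3.9, which now reports no changes. A window that ends at Visit 7 for converters but at final contact for everyone else should be avoided. It would give discontinuers and those who decline the extension extra weeks of observation, and so unequal follow-up if discontinuation differs by arm.
- **Conversion, post-conversion taper and Visit 8 conversion tables:** relabel the former-placebo column 'Placebo converted to PSL' and count it as padsevonil exposure.
- **SAP 10.2:** add serious TEAEs for the Conversion Period.
- **SAP 10.1:** add exposure during Conversion.

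The cost is SAP wording and a few table shells, settled before unblinding. Onset dates and daily dose are already collected, and neither data collection nor study conduct changes.

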5.1.2 Study duration per subject

The total duration of study per subject will be up to 27 weeks with a maximum of 19 weeks exposure to PSL. An additional follow-up echocardiogram will be performed at 6 months (± 1 month) after the last IMP intake only for subjects exposed to IMP for more than 3 weeks and either discontinuing the study or not entering the OLE.

The end of the study is defined as the date of the last SFU Visit (30-days after the last IMP intake) of the last subject in the study. Additionally, the reporting of SAEs will continue until the 6-month follow-up echocardiogram.

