### **2.4.2 Other safety variables**

Other safety variables are as follows:

- Incidence of TEAEs reported by the subject and/or caregiver or observed by the Investigator during the following periods: 16-week Treatment Period, 12-week Maintenance Period, 4-week Titration/Stabilization Period, and 3-week Taper Period
- Number of and reason for subjects requiring premature tapering due to TEAEs
- Number of and reason for subjects requiring a dose reduction during the Stabilization Period due to TEAEs
- Incidence of treatment-emergent SAEs during the following periods: 16-week Treatment Period, 12-week Maintenance Period, 4-week Titration/Stabilization Period
- Changes in clinical laboratory test parameters (including hematology, blood chemistry, and urinalysis)
- Changes in vital sign parameters (including pulse rate, systolic BP, diastolic BP, and respiratory rate)
- Changes in 12-lead ECG parameters
- Physical examination (including body weight) and neurological examination findings

- Changes in Psychiatric and Mental Status
- Occurrence of valvular abnormalities or pericardial effusion changes or other significant abnormalities as identified by 2-dimensional Doppler echocardiogram at each assessment by central reader
- Changes in withdrawal symptoms using Clinical Institute Withdrawal Assessment-Benzodiazepines (CIWA-B) from the End of Treatment Visit (Visit 7) to end of the Taper Period (Visit 8) and end of the SFU Period (Visit 9 [30 days after the last IMP intake]).

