### **3.2.2.2 End of the 16-week treatment period**

The end of the 16-week overall treatment period will be either the date of Visit 7 for subjects completing the Treatment Period, or the date of the early discontinuation visit (EDV), for subjects who discontinued during the Treatment Period. If a subject does not have a Visit 7/EDV, then the date of the final contact will define the end date of the Treatment Period.

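### SAP 10.2 plans no entire-study table of serious TEAEs, although their entire-study incidence is a named primary safety variable

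*SAP*

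**What the plan says.** SAP 2.4.1, repeating Protocol 4.2.1, lists as a primary safety variable: "Incidence of treatment-emergent serious adverse events (SAEs) during the entire study". SAP 2.4.2 lists a different variable under other safety variables: "Incidence of treatment-emergent SAEs during the following periods: 16-week Treatment Period, 12-week Maintenance Period, 4-week Titration/Stabilization Period". The plan therefore treats whole-study and by-period SAE incidence as two variables.

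In SAP 10.2 the planned serious-event table is "Incidence of Serious TEAEs by period (Treatment Period, Titration and Stabilization Period, and Maintenance Period". The bullet directly above it, for all TEAEs, names the same three periods and adds the Conversion Period and the Taper and SFU Period. The breakdowns of SAEs and of fatal TEAEs by relationship come under this lead-in: "The following will be presented for TEAEs during the overall Treatment Period".

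On timing, SAP 3.2.2.2 states: "The end of the 16-week overall treatment period will be either the date of Visit 7 for subjects completing the Treatment Period". For subjects who stop early the period ends at the EDV, and with neither visit it ends at final contact. Table 3-1 starts Conversion on the day after Visit 7. It starts Taper and Safety Follow-up on "The date of the day after Visit 7/EDV or the date of day after Visit 8 if the subject tapered after conversion". Protocol 5.1.2 adds: "The end of the study is defined as the date of the last SFU Visit (30-days after the last IMP intake". SAP 3.9 declares no change from the protocol-defined analyses.

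**The concern.** The serious TEAE table matches the variable in SAP 2.4.2, not the one in SAP 2.4.1. Followed as written, SAP 10.2 produces no explicit summary of one of its three primary safety variables. SAP 3.9 records no change, so this is not a documented choice.

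The time after Visit 7/EDV is not idle time for safety. Protocol 7.2.2 requires monitoring during taper for withdrawal-related events and rebound seizures. In the Conversion Period, subjects randomized to placebo receive padsevonil (PSL) for the first time (Protocol 5.1). A reader who wants serious-event incidence by arm that includes these periods would have to count it from listings.

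**Working it through.** **Step 1. Match each output that could hold serious events to the variable.** The variable needs serious events, over the whole study, as an incidence by arm.

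| SAP output | Events | Window | Gives the variable? |
|---|---|---|---|
| 10.2, sentence on TEAEs by SOC and PT | All TEAEs | Any time in the study | No: the text does not separate serious events |
| 10.2, TEAEs by period | All TEAEs | Five periods, including Conversion and Taper/SFU | No: same reason |
| 10.2, serious TEAEs by period | Serious | Three periods | No: nothing after the Treatment Period |
| 10.2, SAEs and fatal TEAEs by relationship | Serious; fatal | Treatment Period | No: same limit |
| 5.1, AE discontinuations by seriousness | AEs that led to discontinuation | None stated | No: misses every SAE that did not lead to discontinuation |
| 3.1, listings | All | All | No: a listing is not an incidence |

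Serious TEAEs are tabulated in 3 of the 5 windows used for all TEAEs. The number of whole-study serious TEAE tables is 0.

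**Step 2. Check that later events are in scope.** The TEAE definition in SAP 10.2 has no end date. AEs are recorded until the end of the SFU period, 30 days after last intake, and the study ends at the last SFU Visit. A serious event that starts in conversion, taper or follow-up is therefore treatment-emergent and inside the study.

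**Step 3. Size the uncovered time from the schedule** (Protocol Table 5-1: Visit 7 at Week 16, Visit 8 at Week 19/20, Visit 9 at Week 23).

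- Check against the stated durations: 4 baseline weeks + 23 = 27 weeks in the study, and 16 + 3 = 19 weeks of maximum exposure. Both agree with Protocol 5.1.2.
- Completer who tapers: (23 − 16)/23 = 7/23 = 30.4% of the time after first dose. About 3 of these weeks are on tapering investigational medicinal product (IMP) and about 4 are off it.
- Completer who converts: (19 − 16)/19 = 3/19 = 15.8%, all on IMP.
- Placebo-randomized converter: 3 of the 3 weeks of PSL exposure in EP0091. The ceiling is 80 × 3 = 240 subject-weeks, assuming that all 80 planned placebo subjects complete and convert.
- Early discontinuer with an EDV: all taper and follow-up after the EDV. The share depends on when the subject stops.

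**Step 4. Check what a whole-study table alone would show.** SAP 10.2 counts a subject once per category. The whole-study count minus the Treatment Period count therefore gives only subjects whose serious events all came after the Treatment Period. It misses those with an event in both windows, so incidence in Conversion or in Taper/SFU cannot be recovered by subtraction and needs its own display.

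**The case against.** The strongest reply is that little is missing. The 16-week placebo-controlled comparison has its serious TEAE table. SAP 10.2 commits to summarizing all TEAEs at any time in the study, so serious events are counted there. SAP 3.1 promises complete listings. SAP 10.2 also relies on standard sponsor table formats, which the documents do not show, and an all-TEAE shell might carry a line for serious events. All of this stands as a limit on the impact. None of it amounts to a stated commitment to whole-study SAE incidence by arm.

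Four stronger readings are tempting, and the documents do not support them:

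- **The protocol required serious-event displays for taper and conversion.** It did not. The by-period SAE variable in Protocol 4.2.2 names neither period, and the primary variable is one pooled incidence. Adding those periods is a sensible extension that mirrors the all-TEAE bullet.
- **Protocol 13.4.1 is contradicted.** It says that SAE incidence will be summarized and gives no window, but Protocol 13 leaves full details to the SAP. The conflict is with the named variable only.
- **SAEs reported up to six months belong to the variable.** SAP 2.6.2 defines the study end at the last SFU Visit and then says: "Additionally, the reporting of SAEs will continue until the 6-month follow-up echocardiogram". Those later reports lie outside the defined study.
- **About 30% of serious events would go untabulated.** The 30% is a share of scheduled time for one type of subject. The documents do not project how many subjects will taper and give no SAE rate for these periods.

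**Conclusion.** The point holds as a gap in descriptive safety reporting. A primary safety variable named in both documents has no explicit table, and no planned table gives the incidence of serious TEAEs that start in Conversion or in Taper and SFU. The omission is specific to serious events, because the all-TEAE table covers both periods.

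The size can be stated only as time without a serious TEAE table: 30% of post-first-dose time for completers who taper, 16% for converters, and all of the PSL exposure of placebo-randomized subjects who convert. These figures assume the nominal visit weeks, without windows or altered taper schedules. No event count can be projected. A reader might infer that serious events would be lost or that the efficacy conclusions are at risk. Neither follows: the events are collected and listed, and no hypothesis test uses them. The change is worth making because the variable is primary by the plan's own label and the repair is cheap.

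**What to change.** In SAP 10.2:

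1. Add a table of serious TEAE incidence for the entire study (first dose to final contact/SFU), by treatment group, for the Safety Set. Show conversion-phase events of placebo-randomized subjects separately. They are receiving PSL by then, and SAP 10 summarizes by treatment group, so a pooled table could count those events under placebo.
2. Add the Conversion Period and the Taper and SFU Period to the serious TEAE by-period table, as in the all-TEAE bullet above it.

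Two additions are optional and not needed to deliver the primary variable: a fatal TEAE count over the same whole-study window, and a listing of SAEs reported after SFU.

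The cost is one new table and two more periods in an existing one. AEs up to SFU are already on the AE CRF, and Table 3-1 already defines the periods. The optional listing costs more. It would draw on SAE reports from after the AE CRF window (Protocol 11.1.2.3), and reports received after database lock are held in the Patient Safety database (Protocol 11.1.3).
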